**11. Vulnerable Populations**

The research does not contain vulnerable populations.

**12. Local Number of Participants**

20 healthy adults, 18-39 years of age.

**13. Recruitment Methods**

Participants will be recruited from students, faculty, and ancillary staff at Emory University and the Georgia Institute of Technology. Participants will be recruited through word-of-mouth and recruitment flyer. Eligibility will be reviewed through questioning the participants and examination of their skin.

**14. Withdrawal of Participants**

The participant may be withdrawn from the research without their consent if they are not able to follow the protocol.

Given the minimal risk associated with STAR particles and previous history of STAR particles used in humans, there does not appear to be any obvious anticipated circumstances under which participants will be withdrawn from the research without their consent.

If participants withdraw from the research, data collected will be retained and utilized as an intention-to-treat (ITT) analysis.

**15. Risk to Participants**

---

The risks to this study are minimal. We will be applying STAR particles that should puncture the skin, and due to the elastic forces of the skin, will push the particles out. From the time the STAR particles are applied to the skin, the possible risks would be expected to be local skin reactions at the site of STAR particle application including erythema, edema, tenderness, bleeding, and/or bruising.

A systemic reaction would be unlikely to occur, but due to the potential that the application and retention of STAR particles in the skin could facilitate bacterial entry into the skin, in addition to the local reactions listed above, systemic reactions including fever, cough, nausea, vomiting, diarrhea, fatigue, and headaches could also occur. Based on previous human research with STAR particles, local and systemic reactions are unlikely to occur (1). Acute skin reactions (ASRs) will be scored quantitatively with qualitative remarks as needed. The application of the STAR particles is expected to have a minimal risk to the subject. It is possible subjects could describe the placement of the STAR particles as uncomfortable or painful but based on previous human studies (1) this seems less likely. We will take precautions to prevent infections, such as using sterilized or low bioburden materials and wiping the skin with an alcohol swab before the study.

We hypothesize that the STAR particles will not remain in the skin. Our previous research on STAR particles suggests that the risk for application of STAR particles to be minimal (1).

These particles are made of titanium dioxide, a widely used and safe ceramic material found in sunscreens, cosmetics, and paint. STAR particles are designed to incorporate invisibly into topical formulations applied to skin similarly to conventional topical skin products. Based on previous clinical studies and FDA approvals of other drugs/devices using these materials, we therefore expect non-significant risk.

#### **16. Potential Benefits to Participants**

There is no direct benefit to the participant, however, there are potential future benefits to society from the understanding gained by the study.

#### **17. Compensation to Participants**

Study participants will receive a total of \$100 for completion of the study. Participants will receive \$80 at the completion of the in-person study visit. Participants who drive to the visit will be reimbursed for parking in the designated ECC parking area. Participants will also receive \$20 30-days after the in-person study visit assuming they are able to report to the study team if they developed adverse reactions at the application sites 24-hours and 30-days after the in-person study visit.

#### **18. Data Management and Confidentiality**

Data will be stored either electronically in OneDrive or in locked offices and cabinets. The data will be stored locally until we are allowed by the sponsor or Emory to destroy them. Only staff

---

directly involved in completing study procedures will have access to the data. Staff listed on the delegation of authority log will be responsible for receipt and transmission of data. The coordinator or PI/Sub-I will be responsible for transporting the data locally.

If a participant declines to participate *or is ineligible to participate for any or all portions of the study*, the participant will not be assigned a study ID number and the study staff will refrain from collecting any data on the participant.

#### **19. Provisions to Monitor the Data to Ensure the Safety of Participants**

As this study is one with minimal risk, a DSMB will not be needed.

DSMP Requirement	How this Requirement is Met	Frequency	Responsible Party(ies)
Site Monitoring at pre-determined intervals: The Principal Investigator has a responsibility to ensure that the study is following all aspects of the protocol.	There should be a standard operating procedure to review data (whether a sample or 100%) at pre-determined intervals to ensure that there is adequate documentation of critical elements such as eligibility criteria. Monitoring is required at the following timepoints (but may be done more frequently): 

• study initiation

• at least every six months while participants are receiving intervention and

• annually while participants are in follow-up

	Based on risk, a review is required annually when participants have been enrolled.	Delegate a responsible party for each requirement below. Self-assessment is acceptable.* Self-assessment: a process for self-assessment of protocol compliance and data integrity which can be part of an overall DSMP. See Emory's self-assessment tool on this page .
Real-time review of participant data during initial data collection.	Will review the collected data on each participant after collecting the data.	Expectation is that this happens every time you obtain information.	Everyone on the study team responsible for primary data collection.
100% review of consent forms	After each participant is enrolled so that every time a participant is enrolled, his/her CONSENT FORMS will be reviewed for completeness. IN addition, forms will also be re-reviewed when all participants have completed the study.	After each participant is enrolled and after all participants have completed the study.	The Research Study Coordinator & the PI.

**Protocol Title:** Usability of STAR particles in healthy volunteers: A pilot study

Review of credentials, training records, the delegation of responsibility logs (if applicable)	Before enrolling the first participant all credentials of all research study members will be reviewed.	Prior to the enrollment of the first participant.	The Research Study Coordinator & the PI.
Comparison of case report forms (CRF) to source documentation for accuracy and completion	After each enrolled participant completes the one-day study, CRFs will be compared to source documentation for accuracy and completion. In addition, these comparisons will also be made when all participants have completed the study.	After each participant is enrolled and after all participants have completed the study.	The Research Study Coordinator & the PI.
Review of documentation of all adverse events	For any participant who develops an adverse event during the study or after the completion of the study, we will evaluate and compare to other participants. If a similar adverse event occurs for more than 2 participants, we will review the adverse events and not continue with the study until we can ensure the study is safe. Adverse events will be assessed at the time of the study, with reports from the participants, and with follow-up contact between the study team and the participants.	On the day each participant is studied as well as weekly follow-up contact for one month.	The Research Study Coordinator & the PI.
Monitoring of critical data points (eligibility, study endpoints, etc.)	Prior to enrolling participants (eligibility criteria) and after each enrolled participant completes the one-day study, we will monitor the critical data points.	After each participant is enrolled.	The Research Study Coordinator & the PI.
For FDA regulated studies, the following requirements apply:	How this Requirement is Met	Timing, frequency, and intensity of monitoring	Responsible Party(ies)
Monitoring methods (may include centralized, on-site, and self-assessment)	N/A	N/A	N/A

Subject safety:

- Specific subject safety parameters: subjects will report any safety-related issues or concerns to the PI (phone/email when not at a visit) or in person to the PI when at the visit.
  - Most common risk = redness to skin where STAR particles lasting less than 2 hours
  - Less Common Risks = mild irritation or small marks at the site where STAR particles applied
  - RARE risk = skin infection or foreign body growth (100 applications in > 20 participants – This has never occurred)
- Subjects will report observations:
  - During the procedure and 2 hours after the procedure is performed
  - Via follow-up contact from participant to investigating team ANYTIME after completing the study
  - Via follow-up call from investigating team 7 days after the study
- Individual responsible for safety monitoring
  - The PI will be responsible for safety monitoring.
- Subject stopping rules – under what conditions will a subject be removed from study participation and who will make the decision?
  - The study is a one-day study – if the participant has enough discomfort during the study (application of the STARS) the participant can inform the PI that he/she wants to discontinue OR, if the PI determines that the participant is in significant pain, the PI will stop the study
  - If the subject has skin irritation, pain, itching, or infection, a topical medication could be applied to address the symptoms.
  - The minimal risk associated with STAR particles makes it unlikely that a subject would develop any significant local or systemic consequence and therefore, other than subject choice or PI choice, there is not expected to be any condition that should stop the study.
- Study stopping rules - under what conditions will the study be modified or stopped and who will make the decision?
  - If 2 participants have to stop the study to discomfort, the study will be stopped and modifications will be made before resuming the study.
  - Reporting mechanisms (i.e. Deviations, adverse events, UPs)Deviations, AEs, and SAEs will be reported to the IRB by the PI according to Emory IRB reporting guidelines.
- Description of the plan for notifying the IRB of reportable events; whether the sponsor requires reporting above and beyond the Emory IRB reporting requirements, and if so, a description of the requirements and plan for meeting them.
  - We will record from participant questionnaires any adverse events and report to the sponsor (Aldena). If the adverse events are serious they will be reported to the IRB and a plan to modify the application to prevent future SAEs from occurring would be implemented.

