#### **5. Study Intervention/Investigational Agent**

This is a non-randomized, controlled, non-blinded, single-arm pilot study trial, with an adaptive design at mid-trial. After 10 participants complete the study, an interim analysis will be performed and recruitment will either continue with no change to the protocol or, changes may occur in regard to the STAR particle application area, position, pressure, or rubbing cycle in an adaptive design manner.

The trial will be performed in a climatized room and participants will have time to adapt and cool down to decrease risk of modulation TEWL reading.

The investigational agent will be STAR particles made of titanium dioxide, a widely used and safe ceramic material found in sunscreens, cosmetics, and paint. The star-shaped geometry is designed to inhibit complete insertion of the particle into skin, so STAR particles do not remain embedded in the skin. After the arms of the STAR particle puncture the skin, the elastic forces of the skin push the particles out. The STAR particles will be mixed with a gel formulation of the following composition: 0.7%w/w Xanthan Gum + 2.5%w/w Hydroxypropyl methylcellulose + Cyclomethicone and Dimethicone. STAR particles will be produced by Aldena Therapeutics under GMP conditions.

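### The adverse event pause rule applies one count to brief redness and to skin infection alike, and the step to the face cohort does not wait for the 7-day safety calls

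*Protocol*

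**What the plan says.** The pause rule stands in the Section 19 monitoring table, in the row on review of adverse event documentation: "If a similar adverse event occurs for more than 2 participants, we will review the adverse events and not continue with the study" until the team is satisfied that it is safe. The same row has every adverse event evaluated and compared across participants by the coordinator and the PI, with this timing: "On the day each participant is studied as well as weekly follow-up contact for one month".

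The Subject safety list in Section 19 ranks the risks. At one end is "Most common risk = redness to skin where STAR particles lasting less than 2 hours". At the other is "RARE risk = skin infection or foreign body growth (100 applications in > 20 participants – This has never occurred".

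Other provisions in Section 19 bear on the point:
- The study stops for modification if 2 participants stop because of discomfort.
- For serious events: "If the adverse events are serious they will be reported to the IRB and a plan to modify the application to prevent future SAEs". Adverse events in general go to the sponsor, and to the IRB under its reporting guidelines.
- Infection in a participant may be treated topically. Beyond participant or PI choice, no stopping condition is expected.
- Data Integrity sets data monitoring around every 5 subjects, covering pain and local skin findings.
- Participants report observations at these times, among others: "During the procedure and 2 hours after the procedure is performed" and "Via follow-up call from investigating team 7 days after the study".

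Section 5 sets the interim: "After 10 participants complete the study, an interim analysis will be performed and recruitment will either continue with no change to the protocol", or with changes to area, position, pressure or cycles. Section 6.C treats the forearms and one hand of participants 1-10. Section 6.D adds the face for participants 11-20, at 80 kPa for 60 cycles.

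**The concern.** A single count governs two very different kinds of event. Infection and foreign body growth are the events one would want to understand before treating anyone else, yet the rule acts only at the third participant. Brief redness is the expected harmless reaction, yet nothing takes it out of the count. Section 15 has acute skin reactions scored, but the score is not tied to the pause.

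The interim adds to this because it comes just before a new body site. Section 5 waits for 10 participants to complete the study. Section 9 gives each participant one visit and Section 19 calls it a one-day study, so completion can be read as the visit alone. Infection or a foreign body reaction could appear after that day.

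At stake is whether a late local reaction in participants 1-10 must lead to a recorded decision before the face is treated, and whether the study may be held for a reaction it expects.

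**Working it through.** The protocol gives no event rate or operating characteristic for the rule, so there is no figure of its own to reproduce. **All rates below are assumptions**, per participant, with participants independent. X is the number of participants with the event.

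**1. Infection or foreign body growth, participants 1-10.** The rule is met when X ≥ 3. A case occurs with no required hold when X is 1 or 2:
P(1 or 2) = 10p(1−p)⁹ + 45p²(1−p)⁸.
- At p = 0.5%: 0.0478 + 0.0011 = 0.0489.
- At p = 1%: 0.0914 + 0.0042 = 0.0955 (from unrounded terms).

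| Assumed rate | P(1 or 2 cases, no required hold) | P(rule met) |
|---|---|---|
| 0.5% | 4.9% | under 0.1% |
| 1% | 9.6% | 0.01% |
| 5% | 39.0% | 1.2% |
| 10% | 58.1% | 7.0% |

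This counts infection and foreign body growth together. If they were not judged similar to each other, the rule would be slower still.

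**2. What the stated history allows.** No case in more than 20 participants, taken as 0 of 21, gives a one-sided 95% upper bound of 1 − 0.05^(1/21) = 13.3%. The 5% and 10% rows are therefore not excluded, but they are not supported either. The protocol's own ranking as rare points to the top two rows.

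**3. Redness, if logged as an adverse event.** P(X ≥ 3):

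| Assumed rate | First 10 | All 20 |
|---|---|---|
| 10% | 7.0% | 32.3% |
| 30% | 61.7% | 96.4% |
| 50% | 94.5% | over 99.9% |

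**4. Follow-up available before the face cohort.** Section 9 plans enrolment over 3 months. With even enrolment, 90/20 = 4.5 days separate participants. If participant 11 is treated in the next slot, with no time for the interim itself, participant k has (11 − k) × 4.5 days of follow-up.
- Under 30 days: k = 5 to 10 (k = 5 has 27 days, k = 4 has 31.5), so 6 of 10.
- Under 7 days: k = 10 only (4.5 days), so 1 of 10.

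Any time spent on the interim lowers both counts.

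**5. The adverse event window.** Section 4.B ends reporting 5 days after the last visit. The Section 9 table shows 1-30 days, Section 17 refers to 24 hours and 30 days, and Section 19 has a 7-day call and weekly contact for a month. The 5-day window closes before the 7-day call, so a fix has to name the follow-up it relies on.

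**6. Cost of a first-case hold.** If p is the combined rate of all events that would trigger a hold, P(any hold in 20) = 1 − (1 − p)²⁰: 9.5% at 0.5% and 18.2% at 1%.

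**The case against.** The strongest reply is that nothing goes unexamined. Each adverse event is evaluated and compared by the PI and coordinator, on the day and weekly for a month. Local skin findings are monitored around every 5 subjects, so a look may fall near participant 10. Adverse events go to the sponsor and, under its guidelines, to the IRB. The PI may also act at any time. All of this stands. A reader might infer from the pause rule that an infection could reach the face cohort unreviewed, or that serious events wait for a third case. The documents do not support either reading. What is missing is a required hold and a required go/no-go decision. The IRB guidelines are not shown, so any hold they impose cannot be judged.

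On redness, the pause is a review and not a termination, and it could be lifted quickly. Erythema is also captured by photographs and skin scores, and the protocol never says that it is logged as an adverse event. A reader might infer that the study will probably halt for redness. That would follow only if redness is logged and is reasonably common, neither of which is stated.

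Interim decision criteria are commonly left to a statistical analysis plan, which is not shown. The point here is therefore narrower: Section 5 itself sets when the interim happens, and that timing does not include the 7-day follow-up.

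Finally, this is a PI-monitored pilot of 20 people described as minimal risk, and the Section 6.D steps give participants 11-20 two STAR particle sites against eight in participants 1-10. That limits the severity but does not remove the gap.

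**Conclusion.** The point holds as a gap in required action. The count-based rule does not distinguish expected brief redness from infection or foreign body growth. One or two non-serious cases of the latter require no hold, and the first facial application need not wait for the 7-day calls of participants 1-10.

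The size is modest: about a 5% to 10% chance of one or two such cases in the first 10 at assumed rates of 0.5% to 1%. This is the chance of a case without a required hold. It is not the chance of harm or of an unreviewed event. The higher infection rates and all redness rates only illustrate how the rule behaves, and the timing counts rest on even enrolment with no time for the interim. Severity is low, and no endpoint or analysis is affected.

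**What to change.** Four short amendments:

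1. **Section 19, study stopping rules.** Hold enrolment at the first skin infection or foreign body growth at an application site, or the first serious adverse event judged possibly related to the application, at any time up to the end of the one-month follow-up. The hold lasts until the PI has documented a review and a decision to continue, modify or stop.
2. **Section 19, adverse event review row.** Keep the more-than-2-participants rule for all other adverse events, but exclude application-site redness that the participant reports as resolved within 2 hours. The existing 2-hour observation supplies this, as participant report.
3. **Section 5.** Do not treat participant 11 until the PI has reviewed the safety data of participants 1-10, including each 7-day call, and has documented the decision. Later events remain covered by item 1.
4. **Section 4.B.** Change the adverse event window from 5 days to the one-month follow-up, to match the Section 9 table and Section 19.

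The cost is the amendment itself, a possible short hold (about 10% to 18% over 20 participants at assumed combined rates of 0.5% to 1%), and a wait of at most about one week before the face cohort. With even enrolment the added wait is about 7 − 4.5 = 2.5 days, and less if the interim takes time anyway. No new committee, staff, visit or procedure is needed.

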**Data Integrity:**

- Specific data elements to be reviewed include pain (if any) associated with STAR particle formulation insertion, local skin findings at initial placement, and local skin findings during the study.
- Monitoring of data will occur every month after every 5 subjects are enrolled so that data will be monitored 4-5 times during the study depending on how quickly enrollment is complete.
- The PIs will be responsible for data monitoring

**Additional considerations for FDA regulated trials**

- All study activities except production of the STAR particles will be performed on-site
- The study team will self-monitor the study
- The study team will use Emory University's self-monitoring tool found on the CTAC website
- The first subject enrolled will trigger a self-monitoring event
- No Identification of deviations or failures that would be critical to study integrity

**20. Provisions to Protect the Privacy Interest of Participants**

Whenever possible, a study number, rather than the participants name will be used on study records. The participants name and other identifying information will not appear when study results are presented or published. All study documents will be kept in a locked office or secure server.

The sponsor representatives and regulatory authorities (e.g., IRB, OHRP) may inspect all documents and records required to be maintained by the investigator. The study team will permit access to such records.

Subjects will be made aware that all research activities are completely voluntary and will not impact the care they receive. They will also be informed that they are allowed to withdraw from the study at any time.

**21. Economic Burden to Participants**

There will be no costs for the participant associated with the research study.

**22. Informed Consent**

- Participants will be consented by the Principal Investigator in a private space in the ECC.
- There is no standard waiting period before the participant is approached for consent after being told about the study.

- The participant will be reminded throughout the study visit that participation is completely voluntary and that they are allowed to withdraw at any point during the visit or after the visit.
- The study will be explained thoroughly to the participant and the participant will be allowed to ask questions. The study team will give ample time to the potential participants to ask questions and decide whether they would like to participate. The participants will be reminded that the study is completely voluntary and that not participating will not affect their care for their medical condition. The staff performing the informed consent process will also ask the participant questions to verify understanding of the information relayed.

